### 11.3 Interim Analysis

An interim futility analysis of progression-free survival (PFS) by treatment arm will be performed by testing an alternative hypothesis of a 1.5 HR at  $p < 0.05$  when approximately 35% of the expected PFS events in the control arm have been observed. We expect this analysis to occur when approximately 50% of the study sample has been accrued. Unless there are toxicity concerns or extenuating circumstances, the study will not close during this interim assessment. If this alternative hypothesis is rejected at  $p < 0.05$  then the study may be closed to further accrual and the experimental agent declared of no interest for further development. If we fail to reject this hypothesis, the study will complete accrual.

### 11.4 Secondary Endpoints

Secondary endpoints include toxicity, PFS, overall response rate, disease control rate, and duration of response (DoR). The chi-square test will be used to compare toxicity, response rates, and disease control rates and a stratified log-rank test will be used to compare PFS between treatment arms. The distribution of PFS and DoR (among patients who achieve CR/PR) in each treatment arm will be estimated using the Kaplan-Meier method. The overall response rate (confirmed and unconfirmed, complete and partial) in each treatment arm will be assessed in the subset of patients with measurable disease. At least 64 eligible patients in each arm are sufficient to estimate the disease response rate to within 13% (95% confidence interval).

Patients receiving at least one dose of any drug on any arm will be included in the assessment of adverse events. Adverse event monitoring is conducted by the study chairs, disease committee chair, Adverse Event Coordinator and study statistician on an ongoing basis, with notification to the DSMC and CTEP should any concerns arise. Any events reported through the CTEP-AERS system are reported immediately, and reports are sent to the above group for all other AEs on a monthly basis. At least 64 eligible patients in each arm are sufficient to estimate the probability of a particular toxicity to within 13% (95%

confidence interval). Any toxicity occurring with at least a 5% probability is likely (96% chance) to be seen at least once.

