#### 5.2 Prior/Concurrent Therapy Criteria

- a. Patients must have had one and only one prior regimen of systemic therapy for metastatic disease unless the patient meets the criteria in [Section 5.2c](#).
- b. Prior systemic therapy and chemoradiotherapy for treatment of resectable, borderline resectable or locally advanced unresectable disease is allowed and does not count toward prior therapy for metastatic disease.
- c. Patients who received systemic therapy with gemcitabine/nab-paclitaxel for resectable or borderline/locally advanced unresectable disease and progressed with metastatic disease within 3 months of the past dose of systemic therapy are eligible.
- d. Patients must have completed systemic therapy at least 14 days prior to registration, any surgical procedure must have been performed at least 14 days prior to registration, and radiation therapy must be completed at least 7 days prior to registration. Patients must have recovered from major side effects of prior therapies or procedures in the opinion of the local site investigator prior to registration.
- e. Patients must not have received prior irinotecan-based chemotherapy (e.g. FOLFIRINOX or FOLFIRI).
- f. Patients must not have received prior PARP inhibitor therapy including, but not limited to ABT-888, olaparib, rucaparib, and BMN637.

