## 6.0 STRATIFICATION FACTORS

Patients will be randomized using a dynamic balancing algorithm with stratification based on prior systemic treatment for metastatic disease: yes vs no.

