## 11.0 STATISTICAL CONSIDERATIONS

### 11.1 Sample Size and Accrual Goals

The primary objective of the study is to compare overall survival (OS) between the 2 treatment arms. We estimate the median OS of patients treated with FOLFIRI to be 6 months in this population. (113,114) Assuming that the addition of ABT-888 offers an increase in OS to 9 months (HR 1.5), we will need 128 eligible patients, based on a 1:1 randomization, a one-sided type 1 error of 10% and 80% power. Allowing for an approximately 10% ineligibility rate, accrual will be to a total of 143 patients. We expect 28 months of accrual and 10 months of follow-up. Our accrual rate estimate is based on the observed accrual to SWOG study **S1115**.

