### 11.2 Analysis of Primary Endpoint

The primary analysis of OS will be conducted in all eligible patients according to the intent-to-treat principle, using the log-rank test with stratification by prior systemic treatment for metastatic disease. Distributions of overall survival in Arms 1 and 2 will be estimated using the method of Kaplan-Meier. The final analysis will take place upon the observation of approximately 110 deaths.

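### Response and disease control rates are compared with an unstratified chi-square test although randomisation and the OS and PFS tests use a stratification factor; if that factor is prognostic, a little power is lost

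*Combined protocol and SAP*

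**What the plan says.** Section 6.0 names a single randomisation factor: "Patients will be randomized using a dynamic balancing algorithm with stratification based on prior systemic treatment for metastatic disease: yes vs no". Two efficacy tests carry that factor forward. Section 11.2 tests OS "using the log-rank test with stratification by prior systemic treatment for metastatic disease". For PFS, Section 11.4 states that "a stratified log-rank test will be used to compare PFS between treatment arms".

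The same sentence of Section 11.4 treats the binary endpoints differently: "The chi-square test will be used to compare toxicity, response rates, and disease control rates". It mentions neither stratification nor covariate adjustment, and no other section supplies either for the between-arm comparison of ORR or DCR.

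The split between strata is not stated. Section 5.2 says "Patients must have had one and only one prior regimen of systemic therapy for metastatic disease unless the patient meets the criteria in" Section 5.2c, so the 'no' stratum is an exception route and probably the minority. Response rates by stratum are not given, and no significance level is set for these comparisons.

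**The concern.** When arms are balanced on a factor, differences in outcome between its levels no longer contribute to the sampling variation of the treatment contrast. The Pearson chi-square uses the pooled variance, which still contains that between-stratum part. If the factor predicts outcome, the chi-square therefore works with a variance that is slightly too large for the design: its actual size falls a little below nominal and some power is lost.

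At stake is a small loss of efficiency on two secondary endpoints. ORR and DCR are also analysed on a different basis from OS and PFS, and the plan gives no reason for the difference.

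**Working it through.** **1. The plan's own figure.** Section 11.4 states per-arm precision of 13% for the response rate with 64 patients. The worst-case half-width is 1.96 × √(0.25/64) = 1.96 × 0.0625 = 12.25%, which agrees. It concerns each arm separately and does not depend on the between-arm test. The plan states no power for the chi-square comparison, so there is nothing further to reproduce.

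**2. Inputs.** From the documents: 1:1 allocation, 128 eligible patients (64 per arm), and an ORR of 10% used in Section 11.5 as the null rate for the biomarker tables, taken here as a baseline. Assumed because the documents are silent: the share π of patients in the 'no' stratum (10-30%), the rates by stratum (the higher rate placed in the 'no' stratum), a treatment odds ratio of 3, and the alpha. Three two-sided levels are shown: 0.05 (conventional), 0.10 (used for the biomarker tests in Section 11.5) and 0.20 (the two-sided equivalent of the one-sided 10% for OS in Section 11.1).

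**3. Large-sample size of the effect.** With stratum rates p₁ ('no') and p₂ ('yes') and pooled rate p̄ = πp₁ + (1−π)p₂, the ratio of within-stratum to total variance is

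r = 1 − π(1−π)(p₁−p₂)² / [p̄(1−p̄)].

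For ORR 25% vs 10% and π = 0.20:
- p̄ = 0.20 × 0.25 + 0.80 × 0.10 = 0.13
- between-stratum part = 0.16 × 0.15² = 0.0036
- total = 0.13 × 0.87 = 0.1131
- r = 1 − 0.0036/0.1131 = 0.968

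The actual two-sided size at nominal 0.05 is 2[1 − Φ(1.96/√0.968)] = 0.046. Where the stratified test has 80% power, the unstratified test has Φ(1.960 + 0.842 − 1.960/√0.968) = 79.1%. At π = 0.10 the figures are r = 0.980, size 0.048 and power 79.4%.

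**4. Simulation at 64 per arm.** Arms were balanced within strata, with at least 200,000 trials per scenario. Pearson chi-square was compared with Cochran-Mantel-Haenszel (CMH), both without continuity correction. CMH is [Σ(a_k − n₁ₖm_k/N_k)]² / Σ[n₁ₖn₀ₖm_k(N_k−m_k)/(N_k²(N_k−1))], where a_k is the number of responders in Arm 1 and m_k the total number of responders in stratum k.

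| Rates by stratum | Two-sided alpha | Size, chi-square / CMH | Power change from stratifying (points) |
|---|---|---|---|
| ORR 10% vs 25% | 0.05 | 4.3-4.8% / about 4.9% | +1 to +2 |
| ORR 10% vs 25% | 0.10 | not tabulated | +0.5 to +1.3 |
| ORR 10% vs 25% | 0.20 | 20.0-20.6% (chi-square) | about 0 to +0.3 |
| ORR 10% vs 15% | 0.05 | 4.9-5.1% / 4.9-5.0% | about +0.5 or less |
| DCR 50% vs 75% | 0.05 | 4.3-4.5% / 4.9-5.2% | 0 to +0.7 |
| DCR 50% in both | 0.05 | about 4.5% / about 4.5% | about −0.3 to −0.4 (84.9% vs 84.5-84.6%) |

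With ORR 10% in both strata, the two tests differ by only 0.2-0.4 points at two-sided 0.05 (about 61.4% vs 61.6-61.8%). That gap is discreteness, since there is no stratum effect to exploit.

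**5. Extreme strata, as a ceiling** (split 10-50%, two-sided 0.05). ORR 5% vs 30%, a six-fold difference, costs the chi-square 4.6-7.0 points of power. DCR 40% vs 80% costs 1.0-4.6 points. Nothing in the documents suggests differences this large.

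**6. Discreteness.** With no stratum effect and a common rate of 50%, the exact size of the chi-square at 64 per arm is 4.49%; at a common rate of 60% it is 5.4%. Part of the sub-nominal size in the DCR row therefore has nothing to do with the strata.

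**The case against.** The strongest case is that this is a preference, not a defect. An unadjusted chi-square for secondary binary endpoints in a randomised phase II trial is legitimate, and the plan never promises stratified analysis of every endpoint. The gain depends on the factor predicting response, which the documents do not show. It shrinks almost to nothing at the significance level used for OS, and for DCR it turns slightly negative if the factor is not prognostic. No decision rule rests on ORR or DCR, and the planning statement for ORR is per-arm precision.

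All of that stands, and it limits the point to a small, conditional gain in efficiency. It does not remove the point. The sponsor chose this as the trial's only stratification factor and stratified both survival tests by it, so it is reasonable to plan as if it may be prognostic. The worst outcome of stratifying in these scenarios is a loss of about 0.4 points of power.

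A reader might infer more: that the chi-square is invalid, that it inflates type I error, or that Section 11.4 contradicts Section 6.0. None of these follows. Ignoring a balanced factor makes the test conservative if it does anything; the small excursions above nominal size come from discreteness, which affects CMH as well. Using different tests for different types of endpoint is an inconsistency of approach, not a contradiction.

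**Conclusion.** The point holds as a minor, conditional one. ORR and DCR are compared without the randomisation factor. That costs a little power if prior metastatic therapy predicts these outcomes, and nothing if it does not. Under moderate assumptions the cost is at most about 2 points of power for ORR at two-sided 0.05, about 1 point at 0.10 and close to none at 0.20; for DCR it is under 1 point at 0.05.

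These sizes rest on 64 per arm, 10-30% in the 'no' stratum, an odds ratio of 3 and the stratum rates shown. Apart from the 64 per arm, the documents supply none of these. It would be wrong to say without condition that the planned test is conservative or underpowered. The OS analysis, the sample size, the PFS futility rule and the stated 13% precision are unaffected.

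**What to change.** In Section 11.4, replace the chi-square test for ORR and DCR with the Cochran-Mantel-Haenszel test stratified by the Section 6.0 factor, and report the stratified risk difference with its confidence interval. State the alpha and sidedness for these comparisons in the same line, since none is given. Leave the toxicity comparison as it is.

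The cost is one line of text. The factor is needed to randomise each patient, so no new data are required. The Revision #1 memorandum says accrual is closed and all patients are off treatment, but this changes analysis only. It should be fixed before the comparisons are run; if they have already been run, the stratified result can be reported as supportive.

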## 7.5 Full CDUS Reporting Requirement

Because this study contains an investigational drug for which CTEP holds the IND, it falls under CTEP requirements for full reporting. This involves required submission of cycle-specific toxicity and dose information (see [Section 14.4b](#), the **S1513** Treatment Form, and the **S1513** Adverse Event Form). A cycle is defined as 14 days.

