#### 14.4 Data Submission Overview and Timepoints

- a. DAY OF BLOOD DRAW (before or within 5 days after registration prior to treatment):

Submit the following:

Blood specimen as outlined in [Section 15.1c](#).

- b. WITHIN 7 DAYS OF REGISTRATION:

Submit the following:

**S1513** Onstudy Form

**S1513** Baseline Abnormalities Form

Baseline Tumor Assessment Form (RECIST 1.1)

Pathology Reports: Initial diagnosis, metastatic (if done), and fresh biopsy (NOTE: Upload reports via the Source Documentation: Baseline form in Rave®.)

Submit radiology reports from all scans performed to assess disease at baseline. (NOTE: Upload reports via the Source Documentation: Baseline form in Rave®.)

c. WITHIN 28 DAYS OF REGISTRATION:

Tissue specimens as outlined in [Sections 15.1](#) and [15.2](#).

d. WITHIN 14 DAYS AFTER EACH CYCLE OF TREATMENT:

Submit the following:

**S1513** Treatment Form

**S1513** Adverse Event Form

e. WITHIN 14 DAYS AFTER EACH CA19-9 OR CEA TEST (every 4 weeks):

Submit the following:

**S1513** CA19-9 (CEA) Form

f. WITHIN 14 DAYS AFTER EACH DISEASE ASSESSMENT (INCLUDING BOTH ON TREATMENT AND OFF TREATMENT PRIOR TO DISEASE PROGRESSION):

Submit the following:

Follow Up Tumor Assessment Form (RECIST 1.1)

Radiology reports from all scans performed to assess disease (NOTE: Upload reports via the Source Documentation: Follow-up form in Rave®.)

g. WITHIN 14 DAYS OF DISCONTINUATION OF TREATMENT:

Submit the following:

Off Treatment Notice

**S1513** Treatment Form

**S1513** Adverse Event Form

h. WITHIN 14 DAYS OF PROGRESSION/RELAPSE:

Submit the following:

Follow-up Tumor Assessment Form (RECIST 1.1)

Off Treatment Notice (if the patient was still on protocol treatment)

Final **S1513** Treatment Form (if the patient was still on protocol treatment)

Final **S1513** Adverse Event Form

Follow-Up Form (if the patient was off protocol treatment) documenting date, site and method for determining progression/relapse.

Radiology Reports (NOTE: Upload reports via the Source Documentation: Follow-up form in Rave®.)

i. AFTER OFF ALL PROTOCOL TREATMENT, EVERY 3 MONTHS UNTIL 3 YEARS FROM REGISTRATION:

Submit the following:

Follow Up Form

Late Adverse Events Form (if prior to treatment for progression or relapse or a second primary, and prior to non-protocol treatment, the patient experiences any severe [Grade  $\geq$  3] long term toxicity that has not been previously reported)

j. WITHIN 4 WEEKS OF KNOWLEDGE OF DEATH:

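### The between-arm toxicity test in 11.4 has no observation window or exposure adjustment, so it cannot separate higher toxicity per cycle from longer treatment

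*Combined protocol and SAP*

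**What the plan says.** Section 11.4 says "The chi-square test will be used to compare toxicity, response rates, and disease control rates". The analysis set is everyone treated: "Patients receiving at least one dose of any drug on any arm will be included in the assessment of adverse events". The section gives no time window, significance level, per-cycle rate or time-to-first-event method for toxicity. Its sizing statements for toxicity concern precision and detection within an arm, for example "Any toxicity occurring with at least a 5% probability is likely (96% chance) to be seen at least once".

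Treatment continues until progression or symptomatic deterioration, unacceptable toxicity, a delay of more than 4 weeks, withdrawal, or pregnancy or breastfeeding (7.6).

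Collection of adverse events follows treatment and then progression:

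- **On treatment:** the Adverse Event Form is due "WITHIN 14 DAYS AFTER EACH CYCLE OF TREATMENT" (14.4d), with a cycle of 14 days. Section 7.5 adds: "This involves required submission of cycle-specific toxicity and dose information".
- **At discontinuation and at progression:** an Adverse Event Form is due at each (14.4g, 14.4h).
- **Off treatment before progression:** the calendars (9.1, 9.2) mark toxicity notation, with visits every 8 weeks.
- **After all protocol treatment:** the Late Adverse Events Form (14.4i) takes only Grade 3 or higher long-term toxicity not already reported, and only "prior to treatment for progression or relapse or a second primary, and prior to non-protocol treatment".
- **Expedited reports:** Tables 16.1 and 16.2 cover 30 days after the last dose.

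On time to progression, 11.5 assumes a baseline median PFS of 3 months, and 11.3 speaks of "testing an alternative hypothesis of a 1.5 HR".

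**The concern.** With no window stated, the natural reading of a chi-square on toxicity is ever versus never, counted over whatever time each patient was treated and observed. That time is largely governed by progression, and the trial is built on the hope that progression comes later in Arm 1. PFS itself gets a stratified log-rank test, while toxicity, which accrues over the same unequal time, gets a crude proportion. If ABT-888 works, part of any excess toxicity in Arm 1 may reflect more cycles and not more toxicity per cycle. If Arm 1 stops treatment early, the crude proportion may understate its toxicity per cycle.

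Secondary objective 1.2a is to describe toxicity in each arm, and Section 2.0 says the trial should inform later Phase III work. A reader weighing benefit against risk needs both the total burden per patient and the rate while on drug. The planned test supplies only the first.

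**Working it through.** **The plan's own toxicity figures reproduce.** The half-width for 64 patients at a true rate of 50% is 1.96 × √(0.25/64) = 12.25%, which 11.4 states as within 13%. The chance of seeing a 5% toxicity at least once is 1 − 0.95^64 = 96.2%, stated as 96%. Neither figure is in dispute.

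**Inputs from the documents.** 64 eligible patients per arm (128 in total, 1:1; 11.1, 11.4); control median PFS 3 months (11.5); PFS HR 1.5 (11.3), which for exponential PFS means 4.5 months in Arm 1.

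**Assumptions not in the documents.** Exponential PFS; follow-up for toxicity ends at progression; the same constant event hazard λ in both arms; a two-sided 5% Pearson chi-square.

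**Whole-course proportions.** With progression hazard μ, P(at least one event) = λ/(λ + μ).

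- Arm 2: μ₂ = ln 2/3 = 0.2310 per month. Arm 1: μ₁ = 0.2310/1.5 = 0.1540 per month.
- To give 20% in Arm 2, λ = 0.2310 × 0.20/0.80 = 0.0578 per month.
- Arm 1: 0.0578/(0.0578 + 0.1540) = 27.3%.

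Rejection rates come from exact enumeration of the two binomials, 64 per arm:

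| Arm 2 | Arm 1 | Rejection | Rejection if proportions were equal |
|---|---|---|---|
| 10% | 14.3% | 11% | 5.1% |
| 20% | 27.3% | 16.2% | 4.8% |
| 30% | 39.1% | 19.7% | 5.1% |
| 36% | 45.8% | 21.0% | 5.3% |

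Almost all of the rejections are against Arm 1 (16.0 of the 16.2 points in the 20% row). The 36% row is a plausible level: Grade 3 or 4 neutropenia was 35.9% in the Phase I combination study described in Section 2.0.

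**Sensitivity, starting from 20% in Arm 2.**

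- PFS ratio 1.25: 23.8% in Arm 1, rejection 8%. Ratio 1.67 (the 3 to 5 months that 18.4 assumes for BRCA-mutated patients): 29.4%, rejection 24%.
- A common 30-day tail after progression: 26.0%, rejection 12.7%.
- Event hazard present only in the first 2 months: 21.4%, rejection 5.3%. Starting from 36%, it is 38.4% and 6.3%.
- Extra stopping in Arm 1 that brings its median time on treatment to 3.0 months (taking time on treatment as the window): 20% v 20%, no difference. At 2.25 months it is 15.8%, so the direction reverses.
- A two-sided 10% level: rejection 25.4%.

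**What the added summaries do under the same model.** The event rate per unit of treated time is 0.0578 per month in both arms, so a rate comparison shows no difference. For a common window T, P = λ/(λ + μ) × [1 − exp(−(λ + μ)T)]. With T = 56 days (1.84 months), the 20% scenario gives 8.2% in Arm 2 and 8.8% in Arm 1 (rejection 5.3%). The 36% scenario gives 17.5% and 18.6% (5.1%). The window keeps 8.2/20 = 41% of the Arm 2 patients with an event in the 20% scenario, so it omits more than half.

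**The case against.** The strongest reply is that the chi-square answers a legitimate question. Patients treated longer receive more drug, so the extra events are real and total burden matters for benefit and risk. On that view a 16% rejection rate is not Type I error inflation, because the proportions truly differ. This stands, and it is why the whole-course comparison should stay. What it does not answer is whether toxicity per cycle differs, and the plan has no comparison that does.

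A reader might infer that adverse events are collected only while a patient is on protocol treatment. The documents do not support that: toxicity notation continues until progression, a final form is due at progression, and late Grade 3 or higher events are taken afterwards. Collection thins, but the link to time to progression remains.

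A reader might also infer that Arm 1 would look more toxic merely through longer observation, or that it must look more toxic. Neither follows. Exposure lengthens along with observation; early-onset events show almost no effect; and toxicity, delay and withdrawal also end treatment, so the direction can cancel or reverse.

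Finally, objective 1.2a describes toxicity in each arm and does not itself call for a comparison. The comparison rests on one clause in 11.4, no decision rule depends on it, and safety oversight runs through ongoing monitoring and the Data and Safety Monitoring Committee. That limits the weight of the point.

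**Conclusion.** The concern holds in a limited form. The plan states neither a window nor an exposure adjustment for its between-arm toxicity test, and both exposure and ascertainment track an outcome that the trial expects to differ. At the plan's PFS alternative, equal toxicity per unit of time turns 20% into 27% and leads the test to reject about 16% of the time. That size rests on constant event hazards, exponential PFS, observation to progression and an assumed two-sided 5% level, so it lies towards the unfavourable end. It falls to about 5% for events confined to the first 2 months. The direction cannot be known in advance, which is a reason to specify an exposure-aware summary before the data are seen. This is an inexpensive improvement to a secondary analysis and does not affect the primary result.

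**What to change.** In 11.4, state the period over which adverse events count, and keep the whole-course worst-grade chi-square, labelled as a measure of total burden. Add two between-arm comparisons:

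1. Grade 3 or higher events per patient-cycle, or the hazard of the first such event, censored at the end of ascertainment.
2. Worst grade within a common first 8 weeks (Cycles 1-4).

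Read any cumulative incidence at that same 8-week point, because an unrestricted curve carries the same dependence on duration. State the significance level and sidedness used for toxicity.

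The cost is a few sentences and a little more analysis, with no new data collection, since 7.5 already requires cycle-specific toxicity and dose. The 8-week comparison leaves out late and cumulative toxicity, so it should stand beside the per-cycle and whole-course summaries and not replace them.
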